3.4.2 Exposure/Independent Variables of Interest

The exposure of interest is time, e.g., the calendar year of diagnosis, defined in Table 3.

Table 3. Exposure Definition

Exposure	Categories	Definition	Timing
Year of Diagnosis	Each year between 1985 – 2015	Derived using the “diagnosisyear” variable	At index date

3.4.3 Other Covariates/Control Variables

Several demographic and clinical characteristics will be examined in the study cohort. They are summarised in Table 4.

Table 4. Covariate Definitions

Covariate	Categories	Definition	Timing
Ethnicity	White, Non-White or Unknown	Derived using the “Ethnic Group” variable, as follows: White = A (White British), B (White Irish), C (Any Other White Background); Unknown = Z (Not stated), X (Not known) Non-white = All other categories	At index date
Sex	Male, Female or Unknown	Derived using the variable “Sex”, as follows: 1=Male 2=Female	At index date
Vital Status	Alive, Dead or Exit posting	Derived using the “vitalstatus” variable, as follows: A =Alive, D =Dead, X =Exit posting	During follow-up
Age at Diagnosis	0–4 yrs., 5–9 yrs., 10–14 yrs., 15–19 yrs., 20–24 yrs., 25–29 yrs., 30–34 yrs., 35–39 yrs., 40–44 yrs., 45–49 yrs., 50–54 yrs., 55–59 yrs., 60–64 yrs., 65–69 yrs., 70–74 yrs., 75–79 yrs., 80–84 yrs.	Derived using the “fiveyearageband” variable	At index date
SES	1 (least deprived) to 5 (most deprived)	Derived using the IMD quintile variable	At index date

Covariate	Categories	Definition	Timing
Basis of Tumour Diagnosis	Categorisation to be determined in collaboration with NCRAS	Derived using the “basisofdiagnosis” variable to exclude cases diagnosed via autopsy or death certificate	At index date
Site of Tumour	Categorisation to be determined in collaboration with NCRAS	Derived using the “site_ICD10_O2” variable to capture location of malignant melanoma	At index date
Morphology of the Cancer	Categorisation to be determined in collaboration with NCRAS	Derived using the “morph_ICD10_O2” variable to enable description of malignant melanoma	At index date
Behaviour of the Cancer	Categorisation to be determined in collaboration with NCRAS	Derived using the “behavior_ICD10_O2” variable to enable description of malignant melanoma	At index date
T stage	Categorisation to be determined in collaboration with NCRAS	T stage flagged by the registry as the ‘best’ T stage, derived using the variable T_BEST	At index date
N stage	Categorisation to be determined in collaboration with NCRAS	N stage flagged by the registry as the ‘best’ N stage	At index date
M stage	Categorisation to be determined in collaboration with NCRAS	M stage flagged by the registry as the ‘best’ M stage	At index date
Tumour Grade	Well differentiated, moderately differentiated,	Derived using the “grade” variable, as follows:	At index date

Covariate	Categories	Definition	Timing
	poorly differentiated, undifferentiated, or unknown	GX = Grade of differentiation is not appropriate or cannot be assessed G1 = Well differentiated G2 = Moderately differentiated G3 = Poorly differentiated G4 = Undifferentiated / anaplastic	
Clark's Stage	1, 2, 3, 4, 5 or unknown	Derived using the "clarks" variable, as follows: 1, 2, 3, 4, 5, blank	At index date
Breslow Thickness of Tumour	(< or = 0.75 mm, 0.76-1.50 mm, 1.51-4.00 mm, and >4.00 mm ¹⁸)	Derived using the "breslow" variable to enable description of tumour	At index date
Tumour Stage at Diagnosis	Stage 0, I, II, III, IV, or unknown	Derived using the "stage_best" variable to enable description of tumour, as follows: 0, 0A, 0IS = Stage 0 1, 1A, 1A1, 1A2, 1B, 1B1, 1B2, 1C, 1E = Stage 1 2, 2A, 2A1, 2A2, 2B, 2C, 2E, 2S = Stage 2 3, 3A, 3B, 3C, 3E, 3S = Stage 3 4, 4A, 4B, 4C, 4S = Stage 4 6 = missing or unknown	At index date

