3.2.1 Inclusion Criteria

Patients will be included in the study if they meet all of the following criteria:

1. Patients with an ICD-10 code for malignant melanoma
2. Patients aged 18 years or above at their index date

Codes which will be used to identify the population are shown in Table 1.

Table 1. Codes used to identify patients with melanoma

ICD-10 code	Description
C43	Malignant melanoma of skin
C43.0	Malignant melanoma of lip
C43.1	Malignant melanoma of eyelid, including canthus
C43.2	Malignant melanoma of ear and external auricular canal
C43.3	Malignant melanoma of other and unspecified parts of face
C43.4	Malignant melanoma of scalp and neck
C43.5	Malignant melanoma of trunk
C43.6	Malignant melanoma of upper limb, including shoulder
C43.7	Malignant melanoma of lower limb, including hip
C43.8	Overlapping malignant melanoma of skin
C43.9	Malignant melanoma of skin, unspecified

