3.2.2 Exclusion Criteria

Patients will be excluded if they meet any of the following criteria:

1. Unknown gender

2. Patients whose melanoma diagnosis occurred at autopsy

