3.3 Data Source

This study will utilise cancer registration data from PHE. PHE's National Cancer Registration and Analysis Service (NCRAS) is responsible for maintaining a population-based registry of all cases of cancer diagnosed and/or treated in England. NCRAS routinely collects both patient and tumour-level data from more than 500 local and regional datasets. The cancer registration data tables include data on the patient, their diagnosis, tumour characteristics and details of the care and treatment received. This information is submitted by NHS providers to NCRAS on a monthly basis in line with the requirements of the national standard for reporting cancer data, the Cancer Outcomes and Services Dataset (COSD).¹⁴

Specific information provided in the cancer registration data includes the following:

1. Patient tables: Variables include sex, ethnicity, vital status, and cause of death
2. Tumour tables: Variables include age at diagnosis and tumour-related information, such as tumour site and grade, morphology, and histology

Data is available from the 1 January 1985, and there is an approximate one-year lag time between dataset updates.

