3.4 Definitions of Study Variables

3.4.1 Outcomes/Endpoint Variables

The primary outcomes of interest in this study are overall and relative survival¹⁵. Definitions of both the OS and RS are provided in Table 2.

Table 2. Outcome Definitions

Outcome/Endpoint	Definition	Timing
Overall Survival (OS)	Time since the index date (initial diagnosis) +1 until date of death due to any cause. Individuals still alive at the end of follow-up will be censored at the last day of available data.	From the day after index until the last day of available data (during follow-up)
Relative Survival (RS)	RS is defined as the ratio of observed to expected survival, expressed as a percentage. Observed survival at one-year post index will be estimated using the life table method with an actuarial estimator. The expected survival will be estimated using life tables published by the ONS ¹⁶ . The RS will consequently be age-standardised to the international standard cancer patient population. ¹⁷	From the day after index until the last day of available data (during follow-up)

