8 GLOSSARY OF TERMS AND LIST OF ABBREVIATIONS

8.1 Glossary of Terms

Term	Definition
Overall Survival	Overall survival is defined as the length of time between a defined time-point, such as the date of diagnosis of a condition, and the date of death. This is commonly presented as the proportion of patients still alive by a given time-point, estimated using non-parametric methods such as the Kaplan-Meier estimator.
Net survival	Net survival is a hypothetical measurement, defined as patient survival corrected for the effect of other causes of death. In registry studies, net survival is commonly estimated through the calculation of relative survival, both due to the absence of reliable cause of death information as well as the inherent challenges of determining a single cause of death for many patients.
Relative Survival	Relative survival is the ratio of the observed survival rate in a population to the expected survival rate of a similar cohort of people in the general population; matched on age, sex and year of observation. It is commonly expressed as a percentage. It is often used to estimate net or “excess” mortality due to a specific condition, such as cancer, when cause of death information is not known or poorly recorded.
Lead-time bias	Lead-time bias refers to the bias introduced into studies of survival due to the progressively earlier diagnosis of a condition, e.g., due to the introduction of screening.
Stage migration	Stage migration refers to the tendency for cancers to be diagnosed as late-stage or metastatic more readily in later calendar years, due to the use of more sensitive diagnostics or updated staging systems.

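### Table 4 has no age category for eligible patients aged 85 and over, and the protocol does not say which age variable serves eligibility and life-table matching

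*Protocol*

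**What the plan says.** Section 3.2.1 sets the lower age limit: "Patients aged 18 years or above at their index date". No upper limit appears there, in the synopsis or in section 3.2.2, whose only exclusions are unknown gender and "Patients whose melanoma diagnosis occurred at autopsy".

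Table 4 (section 3.4.3) lists the categories of Age at Diagnosis. The list opens with "0–4 yrs., 5–9 yrs., 10–14 yrs., 15–19 yrs" and closes with "75–79 yrs., 80–84 yrs". The definition column reads "Derived using the “fiveyearageband” variable".

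Section 3.3 describes the registry tumour tables: "Variables include age at diagnosis and tumour-related information". It does not say that age is held only in bands.

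For RS, Table 2 states: "The expected survival will be estimated using life tables published by the ONS". The glossary (section 8.1) describes the comparison population as "matched on age, sex and year of observation". Section 4.1.1 leaves the final age-standardisation methodology to the SAP.

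**The concern.** Age is one of two variables that section 4.1.1 singles out as expected key predictors of survival, to be tabulated by calendar year. Baseline demographic characteristics, of which age is one, enter the Cox models. RS is age-standardised. A category list that stops short of the eligible range therefore touches the main analyses, except the death counts and Kaplan-Meier estimates, which need no age.

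The oldest patients are the ones left out of the list. An analyst working from Table 4 could put them in an unclassified row, fold them into 80–84, or lose them from any model that requires age. These choices give different results, and the protocol does not choose between them. If they were lost from the models, the modelled results and the Kaplan-Meier estimates would describe different populations.

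**Working it through.** The plan states no figure on this point, so the check sets the category list against the eligible population.

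**1. Eligible range.** Age 18 upwards, with no upper limit (sections 3.2.1 and 3.2.2).

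**2. Listed range.** Ages 0 to 84 in steps of five: 85 / 5 = 17 bands.
- Three lie wholly below 18 (0–4, 5–9, 10–14).
- One straddles 18 (15–19).
- The other 17 − 3 − 1 = 13 run from 20–24 to 80–84.
- Every eligible age from 85 upwards has no band.
- A patient in the 15–19 band may be 15–17 (ineligible) or 18–19 (eligible), so the band alone cannot apply the criterion.

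**3. Is the list provisional?** Seven other rows of Table 4 (basis of diagnosis, site, morphology, behaviour, and T, N and M stage) say that the categories are still to be agreed with NCRAS. The age row does not; it fixes both the categories and the source variable. It also has no unknown level, unlike grade, Clark's stage and tumour stage. The list ends cleanly and the next cell follows intact, so it reads as complete.

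**4. Where the bands would be used.** Age is tabulated by calendar year and, as a baseline demographic, enters the Cox models; the only age definition the protocol gives for either is Table 4. For life-table matching no age variable is named.

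**5. Illustration for RS, only if the bands were used there.** All inputs are assumptions. Let *s* be the share of patients aged 85+. Expected one-year survival is taken as 0.985 below 85. RS = observed / expected one-year survival, crude and not age-standardised.

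(a) *Patients aged 85+ given the expected survival of 80–84.* Assume *s* = 2–10%, expected survival 0.92–0.94 at 80–84 and 0.82–0.88 at 85+, and true RS 95%.
- Small end (*s* = 2%; 0.94 and 0.88): correct expected = 0.98 × 0.985 + 0.02 × 0.88 = 0.9829; misassigned = 0.98 × 0.985 + 0.02 × 0.94 = 0.9841; RS = 95 × 0.9829 / 0.9841 = 94.88, a shift of −0.12 points.
- Large end (*s* = 10%; 0.92 and 0.82): 0.9685 against 0.9785; RS = 95 × 0.9685 / 0.9785 = 94.03, a shift of −0.97 points.

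(b) *Patients aged 85+ lost from RS.* Assume one-year mortality of 4% below 85 and 20–30% at 85+, *s* = 3–10%, and expected survival at 85+ as in (a). Without them, RS = 0.96 / 0.985 = 97.46%.
- Small end (*s* = 3%, mortality 20%, expected 0.82): observed = 0.97 × 0.96 + 0.03 × 0.80 = 0.9552; expected = 0.97 × 0.985 + 0.03 × 0.82 = 0.98005; RS = 97.46%, a difference of about 0.0 points.
- Large end (*s* = 10%, mortality 30%, expected 0.88): observed = 0.90 × 0.96 + 0.10 × 0.70 = 0.934; expected = 0.90 × 0.985 + 0.10 × 0.88 = 0.9745; RS = 95.84%, a difference of about 1.6 points.

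**The case against.** The best defence is that Table 4 lists labels for a registry field, and an incomplete list of labels deletes no records. Nothing in the protocol codes patients aged 85+ as missing or prescribes complete-case analysis. Section 3.3 names age at diagnosis among the registry variables, and the 18+ criterion itself presupposes either a finer age or selection before extraction. Section 6.1.1 says variable definitions will be modified if needed to meet k-3 anonymisation, so granularity is not final.

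Most of this stands, and it limits what can be said about consequences. It does not remove the gap: the age row is definite, gives these patients no category, and is the only age definition in the protocol.

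A reader might go further and infer that expected survival cannot be matched properly. The documents do not support that. They name the life tables and the matching factors without tying either to the Table 4 bands, and they leave the final standardisation method to the SAP. Nor do they support a claim that five-year bands are too coarse for matching, since they do not say that bands are used for it. The three bands below 15 would simply be empty; removing them is tidying.

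**Conclusion.** The concern holds as a mismatch between the age categories and the eligible population. Patients aged 85 and over are eligible but have no category for the age-by-year tables or for Cox adjustment by this covariate. The 18+ criterion cannot be applied from the listed bands alone. Whether RS is affected depends on which age variable is used for it, and the protocol does not say.

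The effect cannot be sized from the documents. The RS shifts in the working rest wholly on assumed shares and survival, on use of the bands for RS, and on crude rather than age-standardised RS.

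A larger error is easy to infer from crude mortality. With the assumptions in (b), overall one-year mortality would be between 0.97 × 4 + 0.03 × 20 = 4.5% and 0.90 × 4 + 0.10 × 30 = 6.6%, against 4.0% without the oldest patients: a gap of 0.5 to 2.6 points, which would drift if their share changed over the diagnosis years. That is not the size of this problem. Crude all-cause survival is what Kaplan-Meier estimates, and it needs no age. RS divides by an expected survival that is also low at these ages, and its fixed standard weights counter a changing age mix.

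The correction is small and is best made before the data request.

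**What to change.** In Table 4, add a top category covering 85 and over: for example 85–89 and 90+, or a single open 85+ band if k-3 anonymisation requires it. Start the list at 18, so that the first band is 18–19.

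State in the protocol which age variable is used to apply the 18+ criterion and which is used for life-table matching. Single-year age at diagnosis is preferable if obtainable, and section 3.3 suggests the registry may hold it. If only banded age can be released, say so and ask NCRAS to apply the 18+ criterion before release.

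The cost is an edit to one table row, a sentence on the age variable and a small change to the data request. The one real constraint is that k-3 anonymisation (section 6.1.1) may limit how finely age can be supplied, above all at the oldest ages.

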4 STATISTICAL ANALYSIS

4.1 Statistical Analysis Methods

4.1.1 Analysis Plan for Primary Objectives

Objective: *Describe the demographic and clinical characteristics of patients diagnosed with malignant melanoma*

Outcome: *N/A*

Populations: *Overall, within each disease stage and within each SES stratum*

The demographic and clinical characteristics of the overall malignant melanoma cohort will be summarised using descriptive statistics. Means, standard deviations (SD), medians, and interquartile ranges (IQR) will be reported for continuous variables; while counts and percentages will be reported for categorical variables. Descriptions will be stratified by disease stage and SES. Variables anticipated to be key predictors of survival (age and stage at diagnosis) will also be presented stratified by calendar year.

Objective: *Describe one-year overall and relative survival over time among the overall population of malignant melanoma patients and among subgroups of interest (disease stage and SES)*

Outcome: *Number of deaths, OS and RS*

Populations: *Overall, within each disease stage and within each SES stratum*

The overall deaths occurring in the population, as well as within each subgroup, will be presented stratified by calendar year as numbers and percentages.

The non-parametric KM method will be used to estimate one-year OS for the overall study cohort and within each subgroup of interest, stratified by calendar year of diagnosis. The cumulative proportions will be presented together with 95% confidence intervals (CI).

Relative survival will be calculated as the ratio of overall survival for malignant melanoma patients during the one-year period following index date to the overall survival among a comparable cancer free population over the same one-year period. Observed survival will be estimated using life table methods and an actuarial estimator. This estimates a survival probability utilising the total number of events occurring during a specific time interval, in this case one year, as the numerator. The denominator is the effective sample size of the time interval of interest, calculated as the number of people under follow-up at the beginning of that interval minus half of number of people censored during that interval.

Expected survival for the comparable population will be obtained using life tables of the published annual probabilities of survival¹⁶. Estimates of the RS will be age-standardised to the international standard cancer patient population¹⁸, and the final methodology will be detailed within the statistical analysis plan (SAP).

Objective: *Model changes in survival over time*

Outcome: *OS and RS*

Populations: *Overall*

Trends in OS will be modelled using multivariable Cox proportional hazards (PH) models. Cox PH models are a class of survival models that relate the duration of time until an event occurs to covariates that may influence the timing of the event. Covariates in the models will include baseline demographic and clinical characteristics. The key exposure of interest will be calendar year of diagnosis. Trends in RS will be modelled in the framework of generalized linear models (GLMs) using a Poisson assumption for the observed number of death. To model a potential non-linear relationship between the survival (both OS and RS) and the year of diagnosis, smoothing functions such as restricted cubic splines (fractional polynomials) will be used, which implies that the trends will be linear before the first and after the last knot and polynomial and smooth between adjacent knots.

All analyses will be repeated within the subgroups of interest, provided there are enough individuals and consequent deaths to estimate survival within each stratum. Strata where survival cannot be estimated will be presented as blank (“-”) within tables. If numbers allow, differences will be evaluated formally within the Cox/GLM models as relevant using interaction terms.

All analyses will be performed using Stata 12.0 (StataCorp, College Station, Texas) and SAS 9.4 (SAS Institute, Inc., Cary, North Carolina).

4.1.2 Analysis Plan for Secondary Objectives

Not applicable

4.1.3 Analysis Plan for Exploratory Objectives

Not applicable

4.2 Power/Sample Size

All eligible patients will be included. As the dataset has nationwide coverage, all statistics will be calculated directly using the entire population of interest, rather than a sample. Because of this there is no sampling variation, and sample size calculations are therefore not applicable.

5 STUDY LIMITATIONS/STRENGTHS

Analyses of changes in cancer survival over time can be susceptible to lead-time bias and bias due to stage migration as a result of improved diagnostics.¹⁹ Lead-time bias refers to the bias introduced into studies of survival due to the progressively earlier diagnosis of a condition, e.g., due to the introduction of screening. Stage migration refers to the tendency for cancers to be diagnosed as late-stage or metastatic more readily in later calendar years, due to the use of more sensitive diagnostics or updated staging systems. Findings will have to be interpreted bearing such limitations in mind, as well as taking into account the concurrent trends in melanoma incidence and mortality.

Additional limitations include the fact that information on comorbidities and other potentially relevant clinical variables will not be available, meaning that we are limited in the extent to which we can describe patients' characteristics. There is also a relatively high degree of missingness in some variables, notably disease stage, with this variable only being reliably collected by the NCRAS from 2012 onwards.

It is also important to note that secular trends in survival over time can have multiple explanations, and we will not be able to determine the causes of any changes in the survival trends.

However, the study also has several key strengths. The cancer registration data from PHE covers the entire English population, and the results will therefore be generalisable to the population of England. There will also be limited losses-to-follow-up. The dataset further contains variables not commonly available in UK primary- or secondary-care data sources, such as cancer stage. This will allow for a more granular description of mortality trends within subgroups known to have very different survival experiences. The long duration of available data will also allow trends in melanoma mortality to be described over an extensive time-period.

6 STUDY CONDUCT

This study will be conducted in accordance with International Society for Pharmacoepidemiology (ISPE) Guidelines for Good Pharmacoepidemiology Practices (GPP) and applicable regulatory requirements.

6.1 Ethics Committee Review and Informed Consent

6.1.1 Ethics Committee Review

This study will undergo proportionate review by an NHS ethics committee if the data fails to meet k-3 anonymisation as per the ISB1523 anonymisation standards for publishing health and social care data.²⁰ The assessment of the anonymisation standards will be taken by an NCRAS analyst. In the first instance, the study team will seek to modify the study variable definitions to meet k-3 anonymisation standards.

